11.5 Ryan hypoglycemia severity (HYPO) score

The HYPO score involves subject recording of blood glucose readings and hypoglycemic events (BG <3.0 mmol/L [54 mg/dL]) over a 4-week period and recall of all severe hypoglycemic episodes in the previous 12 months. The HYPO score is a scalar quantity based on the severity of hypoglycemic events over a four week period. A hypoglycemic event occurs when a blood sugar reading is less than 54 mg/dL and a series of self-reported questionnaire items determine the severity. The HYPO score is the sum of points awarded to each hypoglycemic event, where a large HYPO score indicates more severity (Ryan, Shandro, K, & al., 2004).

A HYPO score greater than or equal to the 90th percentile (1047) of values derived from an unselected group of type 1 diabetic subjects indicates severe problems with hypoglycemia

The analysis of the raw HYPO score adopts the method for continuous scale variable. Change from baseline will also be calculated and analyzed using the same method.

Subjects with HYPO scores greater than or equal to 1047 will be classified as having severe problems with hypoglycemia, and the analysis of the true rate of this event adopts the method for binary outcome variables.

Statistical Analysis Plan

11.6 *Clarke Score*

The Clarke survey (Clarke, Cox, Julian, Schlundt, & Polonsky, 1995) provides a total score between 0 and 7 (most severe), where scores of 4 or more indicate reduced awareness of hypoglycemia and increased risk of severe hypoglycemic events.

The analysis will treat this variable as continuous and adopts the method for a continuous variable. Change from baseline will also be calculated and analyzed using the same method. The subject will be considered to have reduced awareness if the score is greater than or equal to 4. The rate of reduced awareness will be analyzed using the method for a binary outcome variable.

11.7 *Basal (fasting) and 90-min glucose and C-peptide derived from the mixed-meal tolerance test*

The partial graft function of islet transplantation is indicated by continued C-peptide production. Basal and 90-min glucose and C-peptide derived from the MMTT will be measured at each time point. The glucose levels (fasting and 90 minute) are continuous variables and will be analyzed using the method for continuous scale variables. Change from basal to 90 minutes will be calculated and analyzed using the same methods. Change from baseline for basal, 90 minutes and the difference between 90 minutes and basal will also be analyzed using the same methods.

11.8 *β -score*

The β -score (Ryan, Paty, Senior, Lakey, Bigam, & Shariro, 2005) is an assessment of β -cell graft function after islet transplantation and is treated as a continuous variable and ranges from 0 (no graft function) to 8.

The β -score is generated from a composite scoring system based on fasting plasma glucose values (mmol/L), HbA1c(%), daily insulin consumption (units/kg) or oral hypoglycemic agents use, and stimulated C-peptide levels (nmol/L). For each of these measures, scores of 0, 1, and 2 are assigned to abnormal, intermediate, and normal values, respectively. The β -score is then calculated as the sum of the four scores.

The β -score will be analyzed using the method for a continuous variable.

11.9 *C-peptide/(glucose·creatinine) ratio*

This measure accounts for both the dependence of C-peptide secretion on the ambient glucose concentration and the dependence of C-peptide clearance on kidney function (Zavaroni, Deferrari, Lugari, & al, 1987) (Zerboni, Mangili, & Luzi, 1999). This ratio will be treated as a continuous variable. The analysis of this variable adopts the method for a continuous variable.

11.10 *Acute insulin response to glucose (AIR_{glu}), insulin sensitivity, and disposition index derived from the insulin-modified frequently-sampled intravenous glucose tolerance (FSIGT) test*

The insulin modified FSIGT test will be performed at 75 ± 5 days following the first and final infusion (if applicable). AIR_{glu}, SI and DI, derived from the test, provide a composite measure of β -cell function. AIR_{glu} is calculated as the incremental area-under-the-curve for insulin between 0 and 10 minutes post injection. SI, a measure of insulin-dependent glucose disposal, is derived from Bergman's minimal model using MinMod Millennium software (Pacini & Bergman, 1986) (Saad, Anderson, Laws, & al, 2004). The DI is calculated by AIR_{glu}*SI. The three variables are all continuous and will be analyzed using the method for a continuous variable.

11.11 *Glucose variability and hypoglycemia duration derived from the continuous glucose monitoring system (CGMS)*

CGMS involves the subcutaneous placement of a glucose sensor connected by tubing to a pager-sized monitoring device that stores glucose data obtained every 5 minutes over a 72-hour period (Steja, 2005). Data from a 72-hour period near the target time point will be used to derive the glucose variability and hypoglycemia duration.

The glucose variability is the standard deviation of all measured glucose values and is a continuous variable. This variable will be analyzed using the method for a continuous variable. The data from the 72-hour period are used to derive the number and duration of all hypoglycemic episodes (measured glucose < 3.0 mmol/L [54 mg/dL]). Then the total duration of hypoglycemia can be calculated. The hypoglycemia duration is a continuous variable and is analyzed using the method for a continuous variable. The distribution of the number of hypoglycemic events will be tabled.

11.12 *The percent reduction in insulin requirement*

The percent reduction from the baseline insulin requirement at each time point will be calculated. The analysis of the percent reduction adopts the method for a continuous variable.

12. Analysis of Quality of Life Measures

The analysis of QOL will be conducted for the ITT population. QOL measures are obtained every three months while the patient is on the wait list. Observed values from the last of these prior to transplant will be used as the baseline value. After transplant, QOL measures are obtained at 75 ± 5 days after each transplant (unless a subsequent transplant has occurred), and at one year, 2 years and 3 years after the first and last transplants. Separate analyses will be calculated for each measure at each time point.

12.1 *Generic Measures*

Generic and disease-specific measures will be used to assess QOL. Questionnaires will be completed at enrollment and every 3 months during the screening period and at one year, 2 years, and 3 years after the first and last transplants.

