2.1 Study Design

This is a prospective, single-arm, multi-center study assessing the benefit of islet transplantation in type 1 diabetic (T1D) kidney transplant recipients. The participating centers will treat a total of 24 subjects.

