Table 3.1 provides sample size calculations that use 27% as an estimate of the true favorable outcome rate in the IIT group. Sample sizes for alternative rates are also displayed. These were selected by using 23% (27%-2 times standard error) and 31% (27% + 2 times standard error) where the standard error is the standard error of the estimate from the DCCT study. Sample size calculations assume that an exact one sided test will be used and were calculated using the PASS (Hintze, 2011) sample size program. This table displays the sample sizes required for a one-sided 0.05 binomial test to achieve 80% and 90% power to detect true favorable outcome rates of 40%, 45%, 50%, 55%, and 60% in transplanted subjects compared to the selected rates in the IIT group. If the true favorable outcome rate at one year in IIT subjects is 27% then we would need to transplant 27 subjects to achieve 90% power to detect an improvement to 55% in transplanted subjects. We would need 19 subjects to achieve 80% power to detect 55% versus 27%. We

Statistical Analysis Plan

would need to transplant 40 subjects to ensure 90% power and 27 subjects to ensure 80% power if the true IIT rate is 31% and the true rate in islet transplant subjects is 55%.

Table 4.1: Sample sizes required to achieve 80% and 90% power

Rate in Transplanted Subjects	Power	Historic Rate - IIT		
		23%	27%	31%
40%	90%	64	113	246
	80%	46	84	175
45%	90%	39	64	105
	80%	31	46	76
50%	90%	28	39	59
	80%	21	30	43
55%	90%	21	27	40
	80%	15	19	27
60%	90%	15	19	27
	80%	12	16	17

We have chosen to transplant 24 subjects. This will provide approximately 90% power to detect a difference of 57% favorable outcome rate in islet transplanted subjects versus the estimated 27% favorable outcome rate in the DCCT population. Table 3.2 displays minimal detectable differences for sample sizes of 18, 24 and 30 subjects. With 24 subjects the smallest difference that can be detected with 90% power by a one-sided 5% level test is 57% compared to 27%. The minimal detectable difference is 52% compared to 27% with 80% power.

Statistical Analysis Plan

Table 4.2: Minimal detectable differences if the true IIT rate is 27%

	Power	
	90%	80%
18	62%	57%
24	57%	52%
30	53%	49%

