8.2 Analysis of binary outcome variables

Binary outcome variables will be displayed as percents with 95% exact confidence intervals (Rosner, 1995). The exact confidence interval (P_L, P_U) will be as the solutions to the following equations. If x is the observed outcome (that is, there are x successes in the 24 subjects) then the lower bound will be the solution P_L to the equation

$$0.025 = \Pr \{ \text{at least } x \text{ successes} \mid \text{probability of success} = p_L \} = \sum_{k=x}^{24} \binom{24}{k} p_L^k (1-p_L)^{24-k}.$$

The upper bound will be the solution to the equation

$$0.025 = \Pr \{ \text{no more than } x \text{ successes} \mid \text{probability of success} = p_U \} = \sum_{k=0}^x \binom{24}{x} p_U^k (1 - p_U)^{24-k}.$$

Standard search methods will be used to solve these equations.

8.3 *Analysis of time to event measures*

All time to event measures will be summarized using Kaplan-Meier (product limit) life table methods. Results will be displayed as survival plots. Tables with estimates and 95% confidence intervals for the rates at 1-year, 2-years, and 3-years after the first and last islet transplants will be provided. Separate analyses will be performed for time from first transplant and time from last transplant.

9. Analysis of Demographic and Baseline Measures

9.1 *Baseline Data*

Baseline data collected for the ITT analysis consists of demographic information and medical/physical assessments during the waiting period for islet transplant. These data will be grouped into the following categories:

- Demographic variables
 - Age
 - Sex
 - Race (White, Black, Hispanic, Asian and Other)
- Body Habitus and Quality of Life
 - Body Weight
 - Height
 - Body Mass Index (BMI)
- Diabetes Control
 - Insulin requirement (units/day)
 - HbA1c
 - Fasting and post prandial plasma glucose
 - Fasting and post prandial C-peptide
 - 90-minute C-peptide following consumption of Boost[®] or equivalent
 - 90-minute glucose following consumption of Boost[®] or equivalent
 - Number of severe hypoglycemic events in the last year
 - MAGE score
 - LI
 - Clarke Score
 - HYPO score
 - β -score
 - C-peptide/(glucose·creatinine) ratio

Statistical Analysis Plan

- Measures of Cardiovascular function
 - Carotid intimal thickness
 - Atherogenic profile (fasting lipids, c-reactive protein, serum amyloid A, Apolipoprotein A1, Apolipoprotein B, and the ratio of Apolipoprotein A1 and Apolipoprotein B).
- Measures of Renal function
 - Serum Creatinine

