9.2.2 Analysis of Baseline Diabetes Control Variables

Diabetic control variables include insulin requirement, fasting and post-prandial plasma glucose and C-peptide, glucose and C-peptide 90 minutes post Boost® (or equivalent) glucose challenge, number of hypoglycemic events in the last year, MAGE score, LI, Clarke score, HYPO score, β -score, and C-peptide/(glucose·creatinine) ratio (the ratio of C-peptide to the product of glucose and creatinine).

The distribution of number of hypoglycemic events in the last year will be presented in tabular form. The remaining variables are ordinal scale and will be analyzed as described for continuous variables.

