10.2.3 Additional Post-Hoc Analyses

The HbA1c component of the composite primary endpoint for CIT-06, aimed at controlling HbA1c levels at or below 6.5% or reducing HbA1c levels by 1 percentage point, is based on a minimum rate for efficacy of 27%. This is in contrast to the HbA1c component of the primary endpoint for the CIT-07 trial, aimed at controlling HbA1c levels at or below 7.0%, which is based

Statistical Analysis Plan

on a minimum rate for efficacy of 50%. There are several CIT-06 key secondary outcome measures that, while assessing HbA1c levels at the 6.5% threshold or the 1 percentage point decrease threshold, still use the CIT-07 minimum rate for efficacy of 50%. The study team found the SAP lacking in that it never stipulated that these key secondary outcomes also be evaluated at the minimum rate for efficacy for the CIT-06 primary outcome, 27%. Therefore, we propose to add the three corresponding analyses (from Table 10.1) to the analysis plan in a post-hoc manner. That is, they will not be considered key secondary outcomes, which would otherwise impact the pre-specified plan for adjusting for multiple key secondary comparisons, and they will not replace the current key secondary outcomes, but rather they will be considered additional post-hoc comparisons.

The following table describes the additional post-hoc analyses in terms of Table 10.1, where the additional analyses are broken out from the key secondary analyses table.

Table 10.2 Additional Post-Hoc Analyses

	Additional Post-Hoc Analyses	Minimum Rate for Efficacy
1	At 365 ± 14 days after the last islet transplant (the primary at 365 days after the last transplant): The proportion of subjects with both an $\text{HbA1c} \leq 6.5\%$ and an absence of severe hypoglycemic events from Day 28 to Day 365, or a reduction in HbA1c of 1 point and an absence of severe hypoglycemia from Day 28 to Day 365.	27%
5	At 365 ± 14 days after the first islet transplant: The proportion of subjects with $\text{HbA1c} \leq 6.5\%$.	27%
6	The proportion of subjects with a reduction in HbA1c of at least 1 point	27%

11. Analysis of metabolic outcomes

Separate identical analyses will be reported for outcomes measured at one year after the first and after the last islet transplant, at two years after the first and after the last islet transplant, and at three years after the first and after the last islet transplant.

11.1 *The percent reduction in insulin requirement*

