Subjects will record their total daily insulin dose on self-monitoring diaries. The percent reduction from the baseline insulin requirement ((follow-up minus baseline) divided by baseline) will be computed for each subject for each time point. The analysis of the reduction percentage will use the method described above for a continuous variable.

11.2 *HbA1c*

The primary endpoint requires that either HbA1c at one year after the first transplant is less than or equal to 6.5% or has dropped at least one percent. A secondary endpoint requires that HbA1c is less than 7.0%. The analyses will present the observed percent and 95% confidence intervals for the true percent for the three outcomes: (1) the proportion of subjects with HbA1c $\leq 6.5\%$, (2) the proportion of subjects with HbA1c $< 7.0\%$, and (3) the proportion of subjects with a drop of at least 1.0%.

Additional analyses of HbA1c will adopt the method for a continuous scale variable. Data will be displayed as mean, standard deviation, minimum and maximum. In addition, 95% confidence intervals will be computed as described in the methods section. Change from baseline will be computed and analyzed using the same methods.

11.3 *Mean amplitude of glycemic excursions (MAGE)*

The MAGE requires capillary glucose readings over two consecutive days (a minimum of four readings a day), and is defined as the arithmetic mean of blood sugar increases (or decreases) when both increases and decreases (or vice-verse) at subsequent points in time are greater than 1 standard deviation of the blood sugar for the same two day period (Service, Molnar, Rosevear, Ackerman, Gatewood, & Taylor, 1970). If the MAGE is ≥ 11.1 mmol/L, the subject is considered to have labile diabetes.

The first analysis for this variable directly uses MAGE and adopts the method for a continuous scale variable. In addition, subjects will also be categorized into two groups depending on whether or not the MAGE ≥ 11.1 mmol/L. The analysis of the rate of labile diabetes will be displayed using the methods described for a binary outcome variable.

11.4 *Glycemic lability index*

LI is a measure of blood glucose lability which is based on the change in glucose over time. The LI requires 4 or more daily capillary blood glucose (BG) measurements over a 4 week period.

Statistical Analysis Plan

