For each week, the sum of the squared differences in consecutive glucose readings is divided by the hours apart the readings are determined. Only differences in time that are greater than or equal to 1 hour and less than or equal to 12 hours are used in calculations. This sum is calculated for each of the four weeks and the LI is the mean of the four weekly values (Ryan, Shandro, K, & al., 2004), that is:

$$LI = \frac{1}{4} \times \sum_{i=1}^4 \sum_{j=1}^{N_i} \frac{(\Delta Gluc_{i,j})^2}{\Delta h_{i,j}}$$

where $\Delta Gluc_{i,j}$ is the j^{th} eligible difference of glucose readings in the i^{th} week, $\Delta h_{i,j}$ is the time interval in hours for the j^{th} eligible difference of glucose readings in the i^{th} week. N_i is the total number of the eligible differences of glucose readings in the i^{th} week.

Most subjects have scores under 300 mmol/L²/h·wk⁻¹ with a median of 223 (25 – 75th percentiles 130 – 329 mmol/ L²/h·wk⁻¹). An LI ≥ 433 mmol/ L²/h·wk⁻¹ (90th percentile) indicates serious problems with glycemic lability. The first analysis for this variable directly uses LI and adopts the method described for continuous scale variables. Change from baseline will also be computed and analyzed using the same methods.

Subjects will also be categorized into two groups depending on whether or not the LI ≥ 433 mmol/ L²/h·wk⁻¹. The analysis of the rate of serious problems with glycemic lability will also be analyzed using the method for binary outcomes.

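### The four cut-off rates in SAP 11.3 to 11.6 are planned only after transplant, without a baseline rate or paired analysis, and 11.3 omits the MAGE change score

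*SAP*

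**What the plan says.** The trial has a single arm: "The participating centers will treat a total of 24 subjects" (SAP 2.1).

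The opening of Section 11 sets the time points: "Separate identical analyses will be reported for outcomes measured at one year after the first and after the last islet transplant", and likewise at two and three years. Baseline is not among them.

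The cut-off analyses are:
- MAGE (11.3): "The analysis of the rate of labile diabetes will be displayed using the methods described for a binary outcome variable".
- LI (11.4): "The analysis of the rate of serious problems with glycemic lability will also be analyzed using the method for binary outcomes".
- HYPO (11.5): a score of 1047 or more is classed as a severe problem, and its rate goes to the binary method.
- Clarke (11.6): "The rate of reduced awareness will be analyzed using the method for a binary outcome variable".

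The binary method is in 8.2: "Binary outcome variables will be displayed as percents with 95% exact confidence intervals". It is a one-sample method with no paired element. The MAGE, LI and HYPO cut-off rows in Appendices 8 and 9 hold n, the proportion and its interval.

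Baseline values of all four scores are collected (9.1). For their analysis 9.2.2 says: "The remaining variables are ordinal scale and will be analyzed as described for continuous variables". Appendix 1 has n, mean, s.d., median and range for each score, and no cut-off rows.

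Sections 11.4, 11.5 and 11.6 each add a change-from-baseline analysis of the continuous score. Section 11.3 does not.

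**The concern.** Section 10.2 says the secondary analyses are there to document changes. In a single-arm trial the subject's own baseline is the natural comparator, and a percentage above a cut-off after transplant does not by itself describe change.

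Nor can it be taken for granted that everyone starts above the cut-offs. Section 3 describes an entry route based on HbA1c rather than on severe hypoglycemia. Section 5.1.1 mentions a Clarke score of 4 or more only as a condition for waiving on-study intensive insulin therapy. A low rate at one year can therefore mix resolved cases with subjects who were never affected.

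What is at stake is how readers take four outcomes that the SAP itself labels in clinical terms (labile diabetes, serious glycemic lability, severe hypoglycemia problems, reduced awareness). For MAGE, the simple within-subject change given to its neighbours is also missing.

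**Working it through.** **1. The plan's own figure.** Section 4 states: "With 24 subjects the smallest difference that can be detected with 90% power by a one-sided 5% level test is 57% compared to 27"%. With n = 24 and a null rate of 0.27, the smallest r with P(X ≥ r) ≤ 0.05 is 11. P(X ≥ 11 | 0.27) = 0.0369 and P(X ≥ 11 | 0.57) = 0.904, so the design figure reproduces. The point does not depend on it; it concerns which analyses are specified.

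**2. What is planned for each score.**

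| Score and cut-off | Cut-off rate at baseline | Paired cut-off analysis | Continuous change in Section 11 | Named in 13.1 list | In 13.3 model |
|---|---|---|---|---|---|
| MAGE ≥ 11.1 | no | no | no | no | yes |
| LI ≥ 433 | no | no | yes | no | yes |
| HYPO ≥ 1047 | no | no | yes | no | yes |
| Clarke ≥ 4 | no | no | yes, and key secondary | yes | yes |

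Section 13.3 takes its endpoints from 13.2, whose list names all four scores.

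**3. What a post-transplant rate conveys (assumed counts).** Suppose 4 of 24 have reduced awareness at one year: 4/24 = 17%, exact 95% CI 5% to 37%. With no new cases:
- 6 affected before: 6 − 4 = 2 reversed, 2/6 = 33% (exact 95% CI 4% to 78%).
- 18 affected before: 18 − 4 = 14 reversed, 14/18 = 78% (52% to 94%).

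The cut-off line in the report is the same in both cases.

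**4. What pairing adds (assumed counts).** Suppose 14 of 24 are above the cut-off before, 9 reverse and 1 is new: 14 − 9 + 1 = 6 after.
- Separate intervals: 14/24 = 58% (37% to 78%) and 6/24 = 25% (10% to 47%). They overlap, and the plan would give only the second.
- Reversal proportion: 9/14 = 64% (35% to 87%).
- Exact McNemar on 9 versus 1 discordant pairs: 2 × (10 + 1)/2^10 = 22/1024 = 0.021.

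Six reversals with no new case give 2/2^6 = 0.031, and five give 2/2^5 = 0.0625. A paired analysis can thus be informative with 24 subjects.

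**5. How far the reading depends on the baseline rate.** Assume a normal distribution with the Table 4.4 means and SDs, and MAGE in mmol/L. These are cross-sectional values, not this trial's baseline, and normality is doubtful for HYPO (mean 850, SD 750).
- MAGE: P(Z ≥ (11.1 − 8)/4) = 22%.
- LI: P(Z ≥ (433 − 223)/200) = 15%.
- HYPO: P(Z ≥ (1047 − 850)/750) = 40%.

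A follow-up rate of 2/24 = 8.3% has exact 95% CI 1.0% to 27.0%. That interval contains 22% and 15% but not 40%. The same result would be read differently depending on a baseline rate the plan does not tabulate.

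**6. MAGE in 13.3.** The model has time, transplant status and their interaction, and the pre-post difference is tested if the interaction is significant. A drop of equal size at every matched time point is a status main effect with no interaction. For that pattern the SAP specifies no pre-post test.

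**The case against.** The strongest reply is that the plan does use baseline. Continuous change is planned for LI, HYPO and Clarke, and Clarke change is a key secondary outcome (Table 10.1). Section 13.3 compares pre- and post-transplant profiles in the same subjects for all four scores, MAGE included; it plans means and intervals for the difference at each time point, and the SAP expects the interaction to be significant. Analysing change on the continuous scale is defensible and generally loses less information with 24 subjects. All of this stands.

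A reader might infer that the trial cannot show reversal of these conditions, or that it ignores baseline for them. The documents do not support that. Baseline values are collected, so a paired cut-off analysis remains possible; it is only not pre-specified. In the 4/24 example, the baseline Clarke summary and the Clarke change interval would be expected to differ between the two scenarios, so only the cut-off line is uninformative.

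Other limits also hold:
- Section 3 says the HbA1c entry group may be very small, and it plans subgroup analyses if each group has at least 6 subjects.
- The HYPO cut-off is a 90th percentile from an unselected type 1 population, so it says little about baseline in this selected one.
- Sections 11.8 to 11.11 also lack a change sentence, so MAGE is not alone.
- Section 10.2 makes secondary analyses descriptive, so formal paired tests are not required.

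The remaining gap is not answered by these points. Mean change does not say how many subjects crossed a cut-off that the SAP chose to report, and 13.3 is exploratory and does not analyse the dichotomies.

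**Conclusion.** The point holds in limited form. The SAP pre-specifies neither a baseline rate nor a paired analysis for the four dichotomies, and it leaves MAGE change to an exploratory model with a conditional test. The cut-off rates taken alone do not separate resolution from never having had the problem.

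The consequence is minor. The primary analysis and the key secondary tests are unaffected, and no figure in the SAP is shown to be wrong. The numerical examples rest on assumed counts, on no new cases in the 4/24 example, and on a normal approximation to Table 4.4. They show how the reporting could mislead, not what this trial will find.

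**What to change.** - **Section 11.3:** add the change-from-baseline sentence already used in 11.4.
- **Sections 11.3 to 11.6:** tabulate each cut-off rate at baseline and at each follow-up time point in the same subjects, as a paired shift table. Report the proportion reversed, with an exact 95% interval, among those above the cut-off at baseline.
- **Optional:** an exact McNemar p-value, labelled descriptive and kept outside the key-secondary multiplicity plan.
- **Appendices 1, 8 and 9:** add the matching rows.

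The cost is SAP wording and a few table rows, with no new data collection. The drawback is small denominators for the reversal proportion, and so wide intervals, as 2/6 shows.
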